5.5.2 Nivolumab/IV Placebo

Nivolumab, or matching placebo, is administered IV as a 480 mg via a 30-minute IV infusion on Day 1 of every 28-day cycle, starting on Cycle 2. IV study drug infusion should be prepared as specified in the Pharmacy Manual. Refer to the current version of the IB and/or Pharmacy Manual for complete storage, handling, dispensing, and infusion information.

[figure not shown]
5.6 Dose Modification Criteria

Doses of oral study drug, and/or IV study drug, may be interrupted or delayed for toxicity and other protocol specified criteria. Dose reductions are permitted for oral study drug but not for IV study drug. The assessment for delay or discontinuation should be made separately

for the oral study drug (rucaparib or placebo) and the IV study drug (nivolumab or placebo); however, if toxicity is considered related to all study drugs or if the investigator is unable to determine which study drug is the cause of the AE, then all study drugs in the combination should be delayed and/or discontinued. Dose delay criteria also apply for the placebo of each agent, given the blinded nature of this study. Treatment may be prematurely discontinued due to withdrawal of consent, unacceptable toxicity, disease progression, completion of treatment cycles, or termination of the study, whichever occurs first.

An integrated summary of dose modification guidance by CTCAE Grade v5.0 for events related to IV and/or oral drug is provided below in Figure 2. In addition to the guidance summarized, a dosing delay of > 14 days or > 8 weeks (2 or more consecutive cycles) with oral or IV drug, respectively, requires discontinuation except if approved by the study medical monitor/designee. More detail is provided in Section 5.6.1 (treatment delay and/or interruption), Section 5.6.2 (re-treatment criteria), Section 5.6.3 (dose reduction), and Section 5.6.4 (study drug discontinuation). Please also refer to Appendix 8: AE Criteria for Delay, Resume and Discontinue of Nivolumab.

Figure 2. Integrated Dose Modification Guidance for Events Related to IV and/ or Oral Drug by CTCAE Grade (CTCAE v5.0)

Abbreviations: AE = adverse event; ALT = alanine aminotransferase; AML = acute myeloid leukemia; AST = aspartate aminotransferase; BID = twice a day; CTCAE = Common Terminology Criteria for Adverse Events; DRESS = drug reaction with eosinophilia and systemic symptoms; IV = intravenous; MDS = myelodysplastic syndrome; SJS = Stevens-Johnson Syndrome; TEN = toxic epidermal necrolysis.

5.6.1 Treatment Delay and/or Interruption

5.6.1.1 Rucaparib/Oral Placebo

Treatment with oral study drug should be held if any of the following are observed:

- Grade 3 or 4 drug-related hematologic toxicity
- Grade 3 or 4 drug-related non-hematologic toxicity (except for alopecia, nausea, vomiting, or diarrhea adequately controlled with systemic antiemetic/antidiarrheal medication administered in standard doses according to the study center routines).
 - Grade 3 or Grade 4 ALT/AST elevations should be managed as described in Section 5.6.1.1.1.
- At the discretion of the investigator, oral study drug may be interrupted or continued if new or worsening unexplained pulmonary symptoms suggestive of pneumonitis (including, but not limited to, dyspnea) occur and while evaluation to rule out pneumonitis or confirm such a diagnosis as well as etiology are ongoing; these events should be managed as described in Section 5.7.2.
- In addition, and at the discretion of the investigator, the dose of oral study drug may be held and/or reduced for Grade 2 toxicity not adequately controlled by concomitant medications and/or supportive care.

5.6.1.1.1 ALT/AST ELEVATIONS

- Grade 4 ALT/AST elevations: hold oral study drug until values have improved to Grade 2 or better, then resume oral study drug with a dose reduction. Monitor liver function tests weekly for 3 weeks after oral study drug has been restarted.
- Grade 3 ALT/AST elevations, in the absence of other signs of liver dysfunction, should be managed as follows:
 - Monitor liver function tests weekly until improvement to \leq Grade 2.
 - Continuation of oral study drug with elevation of ALT/AST up to Grade 3 is permitted provided bilirubin is < ULN and alkaline phosphatase is < 3 × ULN.
 - If patient has Grade 3 ALT/AST and continues on oral study drug, and levels do not decline within 2 weeks or they continue to rise, treatment interruption and improvement to ≤ Grade 2 will be required before oral study drug can be resumed, either at the current dose or at a reduced dose.
- ALT or AST > 3 × ULN AND bilirubin > 2 × ULN (suspected DILI).
 - While treatment is interrupted, the patient should be evaluated for the presence of confounding factors including malignant disease in the liver, coadministration of other suspect drugs, cholestasis, and viral or autoimmune hepatitis that could have caused the laboratory abnormalities. Other laboratory investigations of liver function such as international normalized ratio (INR) should be implemented as indicated. If no alternative cause is identified, oral study drug must be permanently discontinued.

- Patients should be followed until all abnormalities have returned to normal, returned to baseline levels, or an alternative cause is found to explain the combination of the increased transaminases and total bilirubin. See Section 8.9.

5.6.1.2 Nivolumab/IV Placebo

IV study drug administration should be held for the following:

- Grade 2 non-skin, drug-related AE, with the exception of fatigue and pancreatitis
- Grade 2 drug-related creatinine (≥ 1.5-3.0 × baseline; > 1.5-3.0 × ULN) or Grade 3 drug-related creatinine (> 3.0 × baseline; > 3.0-6.0 × ULN) abnormalities
 - Baseline is defined as the creatinine value obtained prior to dosing the IV drug on C2D1, or first dose of IV drug, whichever is later

Note: Elevated creatinine is frequently observed with rucaparib monotherapy. Rucaparib is a potent inhibitor of MATE1 and MATE2-K transporters, which are involved in active secretion of creatinine. Rucaparib-mediated creatinine elevation occurs early in treatment (Day 15 of Cycle 1), and is not typically accompanied by elevations in urea (blood urea nitrogen [BUN]). Creatinine elevation resolves with dose holds of rucaparib and recurs with rechallenge. Rucaparib associated creatinine elevation has not been associated with evidence or reports of permanent renal impairment.

- Drug-related AST, ALT, and/or bilirubin abnormalities with the range of AST or ALT > $3 \times \text{and} \le 5 \times \text{ULN}$ or total bilirubin > $1.5 \times \text{and} \le 3 \times \text{ULN}$, regardless of baseline value
 - For participants with the above range of AST or ALT elevations with onset during dosing of the first cycle of oral study drug, IV study treatment hold is not required if AST/ALT elevations begin to resolve before the next scheduled infusion and toxicity is considered to be mainly related to oral study treatment. If the patient has an existing such elevation, and a subsequent AST/ALT increase of more than 20% is observed following infusion of IV study drug, the next IV study drug administration will be held and, if further increase is observed, the Hepatic Adverse Event Management Algorithm will be followed (see Appendix 7). If AST or ALT or total bilirubin elevations are considered mainly related to IV drug, IV drug dosing may resume when laboratory values return to baseline. IV drug should be discontinued at concurrent AST or ALT > 3 × ULN and total bilirubin > 2 × ULN, regardless of baseline value.
 - For participants with ALT or AST elevations > 3 × ULN or total bilirubin > 1.5 × ULN regardless of baseline value that begin after Cycle 3, the Hepatic Adverse Event Management Algorithm will be followed (see Appendix 7).

Note: Rucaparib may cause transient AST and/or ALT elevations (without increased total bilirubin) at Cycle 1, Day 15 that begin to resolve by Day 29, even with continued rucaparib dosing.

Grade 2 or 3 colitis or diarrhea

- Grade 3 pancreatitis with symptoms. Grade 3 increased amylase or lipase without signs or symptoms of pancreatitis does not require dose delay
- Grade 2 rash covering > 30% body surface area or Grade 3 drug-related skin AE. Suspected Stevens-Johnson Syndrome (SJS), toxic epidermal necrolysis (TEN), or drug reaction with eosinophilia and systemic symptoms (DRESS)
- Endocrinopathies met the following criteria:
 - Grade 2 adrenal insufficiency.
 - Grade 2 or 3 hyperglycemia requiring initiation or change in daily management.
 - Grade 1-3 hypophysitis/hypopituitarism that is symptomatic and also associated with corresponding abnormal lab and/or pituitary scan.
 - Grade 2 or 3 hyperthyroidism or hypothyroidism.
- Grade 2 uveitis.
- Grade 2 neurological (other than Guillain-Barre Syndrome [GBS], myasthenia gravis [MG], encephalitis, or myelitis).
- Any grade of encephalitis or myelitis. After workup for differential diagnosis, (ie, infection, tumor-related), if it is not drug related, then dosing may resume when AE resolves.
- Myocarditis with symptoms induced from mild to moderate activity or exertion.
- Other Grade 3 drug-related AE with first occurrence lasting ≤ 7 days.
- Grade 3 drug-related laboratory abnormality (not listed above), with the following exceptions:
 - Grade 3 lymphopenia or Grade 3 increased amylase or lipase without signs or symptoms of pancreatitis does not require dose delay.
 - Grade 3 thrombocytopenia > 7 days or associated with bleeding requires for dose discontinuation.
 - AST, ALT, and/or total bilirubin elevations with a range of AST or ALT > 5 × ULN or total bilirubin > 3 × ULN, regardless of baseline value, will require dose delay or discontinuation. (See Section 5.6.4.2)*
- Any AE, laboratory abnormality, or intercurrent illness that, in the judgment of the investigator, warrants delaying the dose of study medication.

Participants who require dose hold should be re-evaluated weekly or more frequently if clinically indicated and resume dosing during the next scheduled dosing window (Cycle X, Day 1 ± 3 days) after re-treatment criteria are met (Section 5.6.2).

Please refer to Appendix 8: AE Criteria for Delay, Resume and Discontinue of Nivolumab.

5.6.2 Retreatment Criteria

5.6.2.1 Rucaparib/Oral Placebo

For patients who meet treatment interruption guidelines in Section 5.6.1, treatment with oral study drug should be held until the toxicity improves to \leq CTCAE Grade 2. Twice a day dosing may then be resumed at either the same dose or a lower dose, per investigator discretion. If treatment is resumed at the same dose, and the patient experiences the same toxicity, treatment should be interrupted, then resumed at a reduced dose following improvement of the event to \leq CTCAE Grade 2. If the patient continues to experience toxicity, additional dose reduction steps are permitted (Table 4); however, the investigator should consult with the sponsor's medical monitor before reducing to 300 mg BID.

If any blood hematology parameters remain clinically abnormal after 4 weeks of dose interruption, the patient should be referred to hematologist for further investigations. Bone marrow analysis and/or blood cytogenetic analysis should be considered at this stage according to standard hematological practice. For management of anemia, please refer to Section 5.7.1.

5.6.2.2 Nivolumab/IV Placebo

Participants may resume treatment with IV study drug when the drug-related AE(s) improve to Grade ≤ 1 or resolve to baseline value, with the following exceptions:

- Participants may resume treatment in the presence of Grade 2 fatigue and pancreatitis.
- Participants who are suspected with SJS, TEN, or DRESS may resume treatment if SJS, TEN, or DRESS are ruled out and rash reduces to < 10% body surface area.
- For participants with elevated AST, ALT, or total bilirubin elevations, dosing may resume when laboratory values return to baseline and management with corticosteroids, if needed, is complete.
- Drug-related pulmonary toxicity, diarrhea or colitis must have resolved to baseline before treatment is resumed. Participants with persistent Grade 1 pneumonitis after completion of a steroid taper over at least 1 month may be eligible for retreatment if discussed with and approved by the study medical monitor.
- Participants with Grade 2 uveitis may resume treatment if uveitis responds to topical therapy (eye drops) and after uveitis resolves to Grade ≤ 1 or baseline. If patient requires oral steroids for uveitis, then permanently discontinue study drug.
- For visual complaints, patients should be referred to an ophthalmologist following the guidance in Section 7.1.10 of the nivolumab Investigator's Brochure.

Participants with drug-related endocrinopathies adequately controlled with only physiologic hormone replacement may resume treatment after consultation with the study medical monitor.

Participants with Grade 2 neurological (other than GBS, MG, encephalitis, or myelitis) may resume when AE resolves to baseline

If the criteria to resume treatment are met, the patient should restart treatment at the next scheduled timepoint per protocol. However, if the treatment is withheld past the window period of the next scheduled timepoint per protocol to ensure adequate recovery from the adverse event or tapering of immunosuppression, the dosing should continue to be withheld until the subsequent scheduled timepoint.

If treatment is withheld > 8 weeks from the last dose (2 or more consecutive IV drug cycles missed), the subject must be permanently discontinued from study therapy, except as specified in Section 5.6.4.2.

Please refer to Appendix 8: AE Criteria for Delay, Resume and Discontinue of Nivolumab.

5.6.3 Dose Reduction

There will be no dose modifications permitted for IV study drug.

5.6.3.1 Rucaparib/Oral Placebo

The dose reduction steps for oral study drug are presented in Table 4.

Dose escalation upon improvement of toxicity to \leq CTCAE Grade 1 is permitted at the discretion of the investigator.

Dose modifications must be recorded for each patient in the appropriate section of the electronic case report form (eCRF).

Table 4. Oral Study Drug Dose Reduction Steps

Starting Dose	600 mg BID
Dose Level: – 1	500 mg BID
Dose Level: – 2	400 mg BID
Dose Level: – 3 ^a	300 mg BID

Abbreviation: BID = twice a day.

5.6.4 Study Drug Discontinuation

Rucaparib/oral placebo and/or nivolumab/IV placebo should be discontinued according to the criteria specified below. The decision to discontinue each agent may be made independently of one another. However, if the toxicity is considered related to all study drugs or if the

^a Consult with sponsor's medical monitor before reducing to dose level 3. Further dose reduction may be possible but requires consultation with the sponsor's medical monitor.

investigator is unable to determine which study drug is the cause of the AE, then both oral and IV study drug must be discontinued.

5.6.4.1 Rucaparib/Oral Placebo

Oral study drug should be permanently discontinued for any of the following:

- If a participant continues to experience drug-related toxicity despite dose reduction steps to 200 mg BID or if dosing with oral study drug is interrupted for > 14 consecutive days due to toxicity, treatment should be discontinued, with the following exceptions:
 - Dosing delay > 14 days may be allowed if approved by the study medical monitor/designee. Prior to re-initiating treatment in a participant with a dosing delay lasting > 14 days, the study medical monitor/designee must be consulted. Tumor assessments should continue as per protocol even if dosing is delayed.
- Confirmed MDS/AML.
- Any AE, laboratory abnormality, or intercurrent illness which, in the judgment of the investigator, presents a substantial clinical risk to the participant with continued oral study treatment dosing.

5.6.4.2 Nivolumab/IV Placebo

Nivolumab/IV placebo should be permanently discontinued for any of the following:

- Any Grade of GBS, MG and drug-related encephalitis and myelitis
- Any Grade 3 non-skin, drug-related AE lasting > 7 days or that recurs with any duration, with the following exceptions laboratory abnormalities, drug-related uveitis, pneumonitis, myocarditis, bronchospasm, neurologic toxicity, hypersensitivity reactions, infusion reactions, and endocrinopathies:
 - Grade 3 drug-related uveitis, pneumonitis, myocarditis, bronchospasm, neurologic toxicity, hypersensitivity reaction, or infusion reaction of any duration requires discontinuation
 - Grade 3 drug-related endocrinopathies, adequately controlled with only physiologic hormone replacement do not require discontinuation.
 - Grade 3 drug-related laboratory abnormalities do not require treatment discontinuation except:
 - Grade 3 drug-related thrombocytopenia >7 days or associated with bleeding requires discontinuation
 - AST, ALT, or total bilirubin elevations with AST or ALT > 5 × ULN or total bilirubin > 3 × ULN, regardless of baseline value, requires dose delay or discontinuation*
 - *In most cases of such AST or ALT elevation, IV study drug will be permanently discontinued. For participants with such AST or ALT elevations after the start of IV dosing, but on a background of previous elevations on the

first cycle of oral study drug, IV study drug hold is required, but discontinuation is not required, if AST/ALT elevations begin to resolve before the next scheduled infusion, and toxicity is considered to be mainly related to oral study treatment, after the investigator discusses the case with the study medical monitor. Levels will be monitored every 3 days; if they continue to rise more than 20%, the Hepatic Adverse Event Management Algorithm will be followed (see Appendix 7). Treatment with IV drug may be resumed if levels return to an ALT and ALT < 5 × ULN, and total bilirubin < 3 × ULN. If AST or ALT or total bilirubin elevations are considered mainly related to IV drug, and the investigator determines a possible favorable benefit/risk ratio that warrants continuation of study treatment, a discussion between the investigator and the Medical Monitor/designee must occur and approval from Medical Monitor prior to resuming therapy. IV drug dosing may resume when laboratory values return to baseline.

- Any Grade 4 drug-related AE or laboratory abnormality (including but not limited to creatinine, AST, ALT, or total bilirubin), except for the following events that do not require discontinuation:
 - Grade 4 neutropenia ≤ 7 days
 - Grade 4 lymphopenia
 - Isolated Grade 4 electrolyte imbalances/abnormalities that are not associated with clinical sequelae and are corrected with supplementation/appropriate management within 72 hours of their onset
 - Grade 4 drug-related endocrinopathy AEs, such as, hyper- or hypothyroidism, or glucose intolerance and adrenal insufficiency, that resolve or are adequately controlled with physiologic hormone replacement (corticosteroids, thyroid hormones) or glucose-controlling agents, respectively, may not require discontinuation after mandatory discussion with and approval from the study medical monitor/designee.
- Grade 3 or 4 hypersensitivity reaction or infusion reaction. Please refer to Section 5.9 on Treatment of Related Infusion Reactions
- Any event that leads to delay in dosing lasting > 8 weeks (2 or more consecutive IV drug cycles missed) from the previous dose requires discontinuation, with the following exceptions:
 - Dosing delays to allow for prolonged steroid tapers to manage drug-related AEs are allowed.
 - Dosing delays lasting > 8 weeks (2 or more consecutive IV drug cycles missed) from the previous dose that occur for non-drug-related reasons may be allowed if approved by the study medical monitor/designee.

Prior to re-initiating treatment in a participant with a dosing delay lasting > 8 weeks (2 or more consecutive IV drug cycles missed), the study medical monitor must be consulted. Tumor assessments should continue as per protocol even if dosing is delayed. Periodic study visits to assess safety and laboratory studies should also continue every 6 weeks or more frequently if clinically indicated during such dosing delays.

• Any AE, laboratory abnormality, or intercurrent illness that, in the judgment of the investigator, presents a substantial clinical risk to the participant with continued IV study drug dosing.

Please refer to Appendix 8: AE Criteria for Delay, Resume and Discontinue of Nivolumab.

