Appendix 8 Adverse Event Criteria for Delay, Resume, and Discontinue of Nivolumab

Drug-Related Adverse Event (AE) per CTCAE V5	Severity	Action Taken	Clarifications, Exceptions, and Resume Criteria
Gastrointestinal			
Colitis or Diarrhea	Grade 2	Delay dose	Dosing may resume when AE resolves to baseline
	Grade 3	Nivolumab monotherapy: Delay dose	Dosing may resume when AE resolves to baseline
	Grade 4	Permanently discontinue	
Renal			
Serum Creatinine Increased	Grade 2 or 3	Delay dose	Dosing may resume when AE resolves to Grade ≤ 1 or baseline value
	Grade 4	Permanently discontinue	
Pulmonary			
Pneumonitis	Grade 2	Delay dose	Dosing may resume after pneumonitis has resolved to \leq Grade 1.
	Grade 3 or 4	Permanently discontinue	
Hepatic			
Aspartate aminotransferase (AST), alanine aminotransferase (ALT), or total bilirubin (T.bili) increased	AST or ALT > 3x and ≤5x upper limit of normal (ULN) or T.Bili >1.5x and ≤3x ULN, regardless of baseline value	Delay dose	Dosing may resume when laboratory values return to baseline.
	AST or ALT > 5 x ULN or T. bili > 3 x ULN, regardless of baseline value	Permanently discontinue	
	Concurrent AST or ALT > 3 x ULN and T.bili > 2 x ULN, regardless of baseline value	Permanently discontinue	

Endocrinopathy			
Adrenal Insufficiency	Grade 2 adrenal insufficiency	Delay dose	Dosing may resume after adequately controlled with hormone replacement.
	Grade 3 or 4 adrenal insufficiency or adrenal crisis	Delay dose or permanently discontinue	Mandatory discussion with and approval from the Medical Monitor needed prior to resuming therapy. If adrenal insufficiency resolves or is adequately controlled with physiologic hormone replacement, participant may not require discontinuation of study drug.
Hyperglycemia	Hyperglycemia requiring initiation or change in daily management (Grade 2 or 3)	Delay dose	Dosing may resume if hyperglycemia resolves to Grade ≤1 or baseline value, or is adequately controlled with glucose-controlling agents.
	Grade 4	Delay dose or permanently discontinue	Mandatory discussion with and approval from the Medical Monitor needed prior to resuming therapy. If hyperglycemia resolves, or is adequately controlled with glucose-controlling agents, participant may not require discontinuation of study drug.

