Myocarditis	Symptoms induced from mild to moderate activity or exertion	Delay dose	Dosing may resume after myocarditis has resolved

	Severe or life threatening, with symptoms at rest or with minimal activity or exertion, and/or where intervention indicated.	Permanently discontinue	
Other Clinical AE			
Pancreatitis: Amylase or Lipase increased	Grade 3 with symptoms	Delay dose	Note: Grade 3 increased amylase or lipase without signs or symptoms of pancreatitis does not require dose delay. Dosing may resume when patient becomes asymptomatic.
	Grade 4	Permanently discontinue	
Uveitis	Grade 2 uveitis	Delay dose	Dosing may resume if uveitis responds to topical therapy (eye drops) and after uveitis resolves to Grade ≤ 1 or baseline. If patient requires oral steroids for uveitis, then permanently discontinue study drug.
	Grade 3 or 4 uveitis	Permanently discontinue	
Other Drug-Related AE (not listed above)	Grade 2 non-skin AE, except fatigue	Delay dose	Dosing may resume when AE resolves to Grade ≤ 1 or baseline value.
	Grade 3 AE - First occurrence lasting ≤ 7 days	Delay dose	Dosing may resume when AE resolves to Grade ≤ 1 or baseline value.
	Grade 3 AE- First occurrence lasting > 7 days	Permanently discontinue	
	Recurrence of Grade 3 AE of any duration	Permanently discontinue	
	Grade 4 or Life-threatening adverse reaction	Permanently discontinue	
Other Lab abnormalities			
Other Drug-Related lab abnormality (not listed above)	Grade 3	Delay dose	Exceptions: No delay required for: Grade 3 lymphopenia Permanent Discontinuation for: Grade 3
			thrombocytopenia > 7 days or associated with bleeding.

Rucaparib
Clinical Study Protocol: CO-338-087 Amendment 5
16 June 2023

	Grade 4	Permanently discontinue	 Exceptions: The following events do not require discontinuation of study drug: Grade 4 neutropenia ≤ 7 days Grade 4 lymphopenia or leukopenia Grade 4 isolated electrolyte imbalances/abnormalities that are not associated with clinical sequelae and are responding to supplementation/appropriate management within
			72 hours of their onset
Infusion Reactions (manifested by fever, chills, rigors, headache, rash, pruritus, arthralgia, hypotension, hypertension, bronchospasm, or other allergic-like reactions.)			
Hypersensitivity reaction or infusion reaction	Grade 3 or 4	Permanently discontinue	Refer to Section 7.4.4 on Treatment of Related Infusion Reactions

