**CTCAE Grading: Hematology** 

CICAL Grading.	Trematoros			
CTCAE				
Description	Grade 1	Grade 2	Grade 3	Grade 4
Anemia, g/L	100<= AVAL <lln< td="">80<= AVAL <100	AVAL <80		</lln<>	80<= AVAL <100	AVAL <80	
Lymphocyte count decreased, 10^9/L	0.8<= AVAL <lln< td="">0.5<= AVAL < 0.8	0.2<= AVAL < 0.5	<0.2	</lln<>	0.5<= AVAL < 0.8	0.2<= AVAL < 0.5	<0.2
Lymphocyte count increased, 10^9/L		4< AVAL <=20	AVAL >20	
Neutrophil count decreased, 10^9/L	1.5<= AVAL <lln< td="">1<= AVAL <1.5	0.5<= AVAL <1	AVAL <0.5	</lln<>	1<= AVAL <1.5	0.5<= AVAL <1	AVAL <0.5
Platelet count decreased, 10^9/L	75<= AVAL <lln< td="">50<= AVAL <75	25<= AVAL <50	AVAL <25	</lln<>	50<= AVAL <75	25<= AVAL <50	AVAL <25
White blood cell decreased, 10^9/L	3.0<= AVAL <lln< td="">2.0<= AVAL <3.0	1.0<= AVAL<2.0	AVAL <1.0	</lln<>	2.0<= AVAL <3.0	1.0<= AVAL<2.0	AVAL <1.0

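### Protocol Section 5.6 and Appendix 8 conflict on three IV study drug rules, and no visible text says which governs

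*Protocol*

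**What the plan says.** **Liver.** For AST or ALT above 5 × ULN, or total bilirubin above 3 × ULN, Section 5.6.1.2 says the finding "regardless of baseline value, will require dose delay or discontinuation. (See Section 5.6.4.2". Section 5.6.4.2 repeats the choice between delay and discontinuation and makes discontinuation the usual outcome for AST/ALT. It then gives a route back for elevations attributed mainly to IV drug: a favourable benefit/risk assessment, discussion with the Medical Monitor, and "approval from Medical Monitor prior to resuming therapy. IV drug dosing may resume when laboratory values return to baseline". Appendix 8 has a hepatic row for "AST or ALT > 5 x ULN or T. bili > 3 x ULN, regardless of baseline value". Its action is permanent discontinuation, and its exceptions cell is empty.

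**Grade 4 blood counts.** Section 5.6.4.2 permanently stops IV drug for "Any Grade 4 drug-related AE or laboratory abnormality (including but not limited to creatinine, AST, ALT, or total bilirubin"), apart from a listed set of exceptions. The only blood-count exceptions are neutropenia of 7 days or less and lymphopenia. Appendix 8 has a similar list, but its entry reads "Grade 4 lymphopenia or leukopenia".

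**Pneumonitis.** Section 5.6.2.2 states: "Drug-related pulmonary toxicity, diarrhea or colitis must have resolved to baseline before treatment is resumed". Its one relaxation is for persistent Grade 1 pneumonitis, where a patient who has completed a "steroid taper over at least 1 month may be eligible for retreatment if discussed with and approved by the study medical monitor". The Appendix 8 row for Grade 2 pneumonitis allows dosing again at Grade 1 or lower and mentions neither a taper nor approval.

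**Link between the texts.** Sections 5.6, 5.6.1.2, 5.6.2.2 and 5.6.4.2 each refer the reader to Appendix 8. None says which text prevails.

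**The concern.** Both texts are operative protocol instructions for the same drug and the same laboratory or clinical trigger, so where they differ at least one is wrong as written. The practical risk is an IV re-dose that one page allows and another bars, in settings (liver injury, pneumonitis) where re-exposure to a checkpoint inhibitor matters. Pneumonitis is also a designated adverse event of special interest for rucaparib (Section 1.1.1.2.3.1).

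There is a smaller reporting consequence. Section 5 of the ATHENA-COMBO SAP identifies major protocol deviations before treatment codes are released. Without a governing rule, the same re-dose can be classed as compliant or as a deviation.

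**Working it through.** No plan figure is at issue. The check is a side-by-side reading, plus short arithmetic on exposure and timing.

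**Step 1. Compare the rules.**

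| Trigger | Section 5.6 | Appendix 8 | Stricter text |
|---|---|---|---|
| Isolated Grade 3 AST/ALT > 5 × ULN or bilirubin > 3 × ULN, mainly IV-related | Delay possible; resume at baseline with Medical Monitor approval | Permanently discontinue | Appendix 8 |
| Grade 4 leukopenia | Permanently discontinue (not a listed exception) | Exempt | Section 5.6 |
| Resuming after Grade 2 pneumonitis | Baseline; or persistent Grade 1 after taper ≥ 1 month with approval | Grade 1 or lower, no further condition | Section 5.6 |

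The count is Appendix 8 in 1 of 3 and Section 5.6 in 2 of 3. Relying on either text alone therefore does not deliver the stricter rule throughout.

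**Step 2. Narrow each conflict to where it really exists.**

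*Liver.* The grading tables in Appendix B of the ATHENA-COMBO SAP give, for a normal baseline, Grade 3 AST/ALT as > 5 to 20 × ULN and Grade 3 bilirubin as > 3 to 10 × ULN. Above those limits the event is Grade 4, and Section 5.6.4.2 also stops the drug. For concurrent AST/ALT > 3 × ULN and bilirubin > 2 × ULN, Section 5.6.1.2 and Appendix 8 both stop it. The conflict is left in two bands:
- AST or ALT > 5 to 20 × ULN with bilirubin ≤ 2 × ULN;
- bilirubin > 3 to 10 × ULN with AST and ALT both ≤ 3 × ULN.

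The empty Appendix 8 cell is hard to read as shorthand. Where that table intends monitor-approved resumption, as in its Grade 4 endocrine rows, it says so.

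*Leukopenia.* The SAP row "White blood cell decreased, 10^9/L" puts Grade 4 below 1.0. Grade 4 neutropenia lasting more than 7 days is outside the exemption in both texts. The conflict therefore concerns a total count below 1.0 without such prolonged neutropenia.

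*Pneumonitis.* The texts differ for a patient who has improved to Grade 1 but not to baseline, and who lacks the one-month taper or the approval. Appendix 8 lets her resume; Section 5.6.2.2 does not.

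**Step 3. Look for a governing rule.** The four cross-references to Appendix 8 set no precedence. Appendix 7's hepatic notes point to the protocol's delay and discontinuation criteria, but Appendix 8 is itself part of the protocol, so they do not choose between the two. One further sign that Appendix 8 was not reconciled with this protocol is its infusion-reaction row, which cites Section 7.4.4. That section is the Cycle 3-and-beyond visit schedule; infusion reactions are in Section 5.9.

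**Step 4. Size and timing.**
- Patients who could receive active nivolumab: 400 (Arm A) + 100 (Arm C) = 500 of about 1000 planned.
- Event frequency cannot be computed from the documents.
- Section 9.2.2 expects randomization to close in the third quarter of 2020. Last dosing = close + up to 3 days + 28-day Cycle 1 + 24 months. From 1 July 2020 this gives about 1 August 2022; from 30 September 2020, about 31 October 2022.
- Amendment 5 is dated 16 June 2023, which is 319 to 228 days later, or about 10.5 to 7.5 months.

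**The case against.** The case for leaving this alone has substance. A site can satisfy both texts by taking the stricter action. Section 5.6 points to Appendix 8 four times, so missing it means skipping an instruction. Hepatic re-dosing already needs a benefit/risk assessment, Medical Monitor approval and return to baseline. Investigators may hold or stop IV drug whenever they see clinical risk. On the expected timeline, edits to Amendment 5 would reach few or no patients still being dosed. These arguments limit the severity; they do not make the two texts agree.

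It could also be said that Appendix 8 only selects the discontinuation option that Section 5.6.4.2 leaves open. That does not work for the liver rule, because the route to resumption in Section 5.6.4.2 would then have no use.

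A reader might infer several stronger points that the documents do not support:

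- *Grade 3 colitis or diarrhea as a fourth conflict.* Section 5.6.1.2 lists it as its own hold and attaches the 7-day limit to other Grade 3 events. The Appendix 7 gastrointestinal note and Appendix 8 also allow delay. Only a broad reading of the Grade 3 rule in Section 5.6.4.2 adds a stop.
- *Section 5.6 prevails.* Its internal consistency on the liver rule does not establish that, and the Appendix 7 hepatic notes do not either (Step 3).
- *The leukopenia exemption is an error to delete.* Section 5.6.4.2 itself exempts short Grade 4 neutropenia and Grade 4 lymphopenia, both components of the white count, so the exemption may be intended. Intent is unknown.

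**Conclusion.** The conflict is real on three rules: isolated Grade 3 liver elevations attributed mainly to IV drug, Grade 4 leukopenia, and resumption after Grade 2 pneumonitis. It does not extend to Grade 4 or concurrent liver elevations. No claim is made for elevations attributed mainly to oral drug.

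Severity is minor. Section 5.6 applies the delay criteria to placebo as well, so no bias between arms is shown. Alpha, power and the primary test are unaffected, and the ATHENA-COMBO SAP excludes no patient from efficacy analysis for a major deviation. Inferring that patients were re-dosed unsafely, or that results are compromised, would go beyond the documents.

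The conclusion rests on the visible text. Figure 2 and the Appendix 7 algorithms are not shown and could contain a precedence rule or further resumption conditions. The view that little or no dosing remained assumes that randomization closed as expected in the third quarter of 2020. Section 7.1 of the ATHENA-COMBO SAP is consistent with this, since it expects all patients to be off treatment at the visit cut-off. Whether earlier protocol versions carried the same conflicts cannot be determined here.

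**What to change.** Add one sentence to Section 5.6: *Where Section 5.6 and Appendix 8 differ, the stricter rule applies.* This needs no guess about intent. Then align the rows:

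1. **Pneumonitis:** bring the Appendix 8 row to the Section 5.6.2.2 conditions.
2. **Liver:** the sponsor states whether monitor-approved re-dosing after an IV-related elevation is intended, and makes Section 5.6.4.2 and Appendix 8 match.
3. **Leukopenia:** the sponsor states whether Grade 4 leukopenia is exempt, and makes both exception lists match.
4. **Typographical:** in Section 5.6.4.2, correct *ALT and ALT* to *AST and ALT*.

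No colitis edit is needed. If IV dosing deviations are classified under SAP Section 5, the protocol version in force on the event date should be used, so that a later clarification is not applied retrospectively.

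The cost is one sentence, three alignments and one typographical correction, with no new data. The downside is that, under the stricter-rule default, a few patients may stop IV drug who could have resumed, until the sponsor settles items 2 and 3.
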